The non-vitamin K oral anticoagulants (NOACs) are a new group of drugs which have been recently approved for use as blood thinners. They have a faster onset of action compared to warfarin and unlike warfarin, they do not need frequent monitoring. Apixaban and Rivaroxaban both have a similar mechanism of action. They inhibit Factor 10 which a clotting factor. They are the most commonly prescribed NOACs at Einstein Medical Center Philadelphia. We intend to serially monitor the kidney function by measuring the serum creatinine and urinalysis of 40 high risk patients who are recently started on either apixaban or rivaroxaban over a six month period. This will enable us to discover what proportion of patients actually develop ARN after starting a NOAC.

2) Project Objectives and Hypotheses:

Determine the incidence of ARN in high risk patients on rivaroxaban or apixaban (Factor 10 inhibitors).

Hypothesis - the incidence of ARN with apixaban or rivaroxaban is less than the previously reported incidence of ARN in warfarin.

- Describe demographic and urinalysis-associated predictors of ARN in patients on rivaroxaban or apixaban (Factor 10 inhibitors)

3) Background/Significance of Research (*Provide the scientific or scholarly background and rationale for the research based on the existing literature (include references). Describe relevant prior experience and gaps in current knowledge. Describe any relevant preliminary data. Explain the significance of the research in terms of why it's important and how it will add to existing knowledge.*):

Anticoagulation-related nephropathy (ARN) is an understudied renal complication of anticoagulant therapy that is characterized by acute kidney injury (AKI) defined as an increase in baseline serum creatinine ≥ 0.3 mg/dL, without any alternate etiology, in the setting of a supra-therapeutic International Normalized Ratio (INR) greater than 3.0 [1-7]. ARN has mainly been studied in relation to warfarin, it usually occurs in the first two months of starting anticoagulant therapy and retrospective studies have estimated the prevalence to range from 16% to 37% [4-6]. The strongest risk factor for ARN is pre-existing chronic kidney disease (CKD); other risk factors include older age, diabetes mellitus and hypertension [1,4]. Patients with ARN have an accelerated progression of CKD and a retrospective study of more than 15,000 patients on warfarin showed a 65% increase in mortality in patients with ARN [4,6].

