Secondary endpoint - Urinalysis measurements (particularly hematuria and proteinuria) will be analyzed for correlation with the incidence of ARN. Demographic variables including age and race will be analyzed in contingency tables using Fisher's exact test to ascertain if they are significant for the primary outcome.

- ii. Describe any primary or secondary safety endpoints (*e.g. any disease or symptom that would result in the withdrawal of that subject from the study*): Subjects will be censored from the study if anticoagulation is withdrawn for any clinical reason

e. Human Research Methods:

- i. Describe and explain the study design (*e.g. randomized, double-blind, placebo-controlled clinical trial or retrospective chart review*):

This is a prospective observational study designed to determine the incidence of ARN in 40 adult patients recently initiated on rivaroxaban or apixaban at Einstein Medical Center Philadelphia.

- ii. Describe all research activities involved in this protocol, including a study visit timeline if appropriate:

Baseline demographic data, past medical history, current medication list and baseline laboratory records (taken within the last three months) will be obtained from the patient's hospital chart and the electronic medical record. Serum creatinine and urinalysis measurements will then be repeated at monthly intervals for the first three months and then at the six-month mark. These laboratory tests will be drawn at Einstein's Klein building Suite 100 by a trained phlebotomist.

If AKI, defined as an increase in baseline serum creatinine ≥ 0.3 mg/dL from baseline, is noted in any study participant, the patient and his primary care physician or cardiologist will be notified both verbally and through a detailed letter. A standard clinical evaluation and work up will then be performed by the patient's primary care physician or cardiologist as part of the patient's usual care with referral to a nephrologist if necessary. The research team will then be notified of the result of this work up.

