- i. Describe steps that will be taken to secure the data (e.g. training, authorization of access, password protection, encryption, physical controls, certificates of confidentiality and separation of identifiers and data) during storage, use and transmission: As stated above, a study participant list containing identifiable data will be password protected and stored on the Einstein system. This list will only be able to be accessed by members of the research team. All other data will be stored in a separate database with unique but unidentifiable identification numbers. At the termination of the study the initial study participant list will be deleted.
- ii. Describe the data analysis plan, including any statistical procedures and method for determining the sample size for the study:

Incidence of ARN is the primary outcome of this study and this is based on a documentation of AKI (defined as an increase in baseline serum creatinine ≥ 0.3 mg/dL), in the absence of any other obvious etiology for the AKI identified after a standard clinical evaluation and work up by the patient's primary care physician, cardiologist or nephrologist. This incidence will be expressed as a percentage.

Urinalysis measurements (particularly hematuria and proteinuria) will be analyzed for correlation with the incidence of ARN. Demographic variables including age and race will be analyzed in contingency tables using Fisher's exact test to ascertain if they are significant for the primary outcome.

There is no data at all in the literature for the incidence of ARN with rivaroxaban or apixaban and we short-listed that number (40) based on the reported incidence for warfarin (17-37%). We are selecting the patients at highest risk (elderly, CKD) for anticoagulation-related nephropathy (ARN) and we expect that the incidence we obtain will be the highest for the population we are studying.

In terms of precision, we will calculate confidence intervals of the proportional incidence using Stata (command line `cii 40 (incidence)`). If the incidence is zero, Stata calculates the 95% confidence interval based on our sample size as 0-9%. If we only find 2 cases of ARN, Stata calculates the point estimate incidence at 5% with 95% confidence interval as 0.6% - 17%, If we find 10 cases of ARN, Stata calculates the point estimate incidence as 25% with 95%

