confidence interval as 13% to 41%, etc. Our sample is elderly, CKD subjects at higher risk hence we expect a higher incidence than in the normal population, hence a negative result will suggest very low risk in the general population.

- iii. Describe where and how data will be stored locally: Data will be stored in password protected spreadsheets on the Einstein computer network.
- iv. Specify how long data will be stored locally: 6 years after publication of the study
- v. Specify who will have access to the data locally: The research team members.
- vi. Describe process that will be followed to ensure accuracy of collected data: All data will be checked twice upon entering it into the database to ensure accuracy. All calculations and statistical tests will be confirmed by both members of the team.
- vii. Will data be sent out or received: No Yes
 - a. Who is responsible for receipt or transmission of the data? N/A
 - b. How will the data be transported? N/A

h. Provisions to monitor the data for the safety of subjects (Required only when Human Research involves more than minimal risk):

- i. Describe plans to periodically evaluate the data collected regarding both harms and benefits to determine whether subjects remain safe. Include what data will be reviewed, who will review the data and when the data will be reviewed:

This research has no additional risk above and beyond that of a blood draw and urine collection. Blood draws for serum creatinine assay will be performed by a trained phlebotomist using standard techniques. Any problems encountered during blood draws will be reported to the research staff and will be reviewed by the entire research study team as soon as they occur to determine if and when the event needs to be reported to the IRB, and if the protocol and/or consent document require modification. Each safety data will be reviewed by at least 2 members of the research team and all events will be reviewed after every 10 patients are recruited.

i. Withdrawal of Subjects:

- i. Describe the anticipated circumstances under which subjects will be withdrawn from the research without their consent: Subjects will be censored from the study if anticoagulation is withdrawn for any clinical reason

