- ii. Describe the procedures that will be followed when subjects withdraw from the research (or request that their data be withdrawn), including partial withdrawal from procedures with continued data collection: If a patient is censored from the study, all of their data will be removed from the study participant list and study database.

7) Risks to Subjects:

- a) List the reasonably foreseeable risks, discomforts, hazards or inconveniences to the subjects. For each indicate the probability, magnitude, and duration when possible (consider physical, psychological, social, legal and economic risks as well as risks related to confidentiality): This research has no additional risk above and beyond that of a blood draw and urine collection. Blood draws may rarely cause pain, bleeding and bruising. Blood draws for serum creatinine assay will be performed by a trained phlebotomist using standard techniques.
- b) If applicable, indicate which procedures may have risks to the subjects that are currently unforeseeable: None
- c) If applicable, indicate which procedures may have risks to an embryo or fetus should the subject or the subject's partner be or become pregnant: None
- d) Describe, if applicable, the process that will be followed if a subject or the subjects' partner becomes pregnant while participating in the study: None
- e) If applicable, describe risks to others who are not subjects: None

8) Potential Benefits to Subjects

- a) Describe the benefits that individual subjects may experience (include when possible the probability, magnitude and duration of the potential benefits) or indicate if there is no direct benefit: If a patient develops ARN, this study ensures that the condition will be detected and the patient will receive a comprehensive work up in standard care. The benefit to the patient is that they are receiving extra monitoring for this condition.

9) Medical care and compensation for injury (Required for Greater than Minimal Risk Studies Only):

- a) Describe any provisions for medical care and available compensation in the event of a research related injury: N/A
- b) Provide the contract language, if any, relevant to compensation for research-related injury: N/A

10) Cost to participants:

- a) Describe any actual or potential cost that subjects may incur through participation: There are no costs that the subject may incur.

11) Provisions to Protect the Privacy Interests of Subjects:

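### Stopping anticoagulation deletes the participant's whole record, including any AKI or ARN already documented, so primary-endpoint events can vanish from the incidence

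*Protocol*

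**What the plan says.** The rule is built from two places in the Protocol's Study Design section.

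- **Trigger.** Under Study Endpoints (d.ii), and again under Withdrawal of Subjects (i.i): "Subjects will be censored from the study if anticoagulation is withdrawn for any clinical reason".
- **Consequence.** Under Withdrawal of Subjects (i.ii): "If a patient is censored from the study, all of their data will be removed from the study participant list and study database". The form's prompt there asks about withdrawal procedures, "including partial withdrawal from procedures with continued data collection"; the answer provides only for removal.

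Three other parts bear on it.

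- **Endpoint.** The primary outcome is the percentage of participants with ARN, meaning a creatinine rise of at least 0.3 mg/dL with no other obvious cause after work-up (d.i and g.ii). The Protocol Abstract gives the purpose: "This will enable us to discover what proportion of patients actually develop ARN after starting a NOAC".
- **Notification.** When AKI is found, "the patient and his primary care physician or cardiologist will be notified both verbally and through a detailed letter" (Human Research Methods, e.ii).
- **Interpretation.** The hypothesis in section 2 is that "the incidence of ARN with apixaban or rivaroxaban is less than the previously reported incidence of ARN in warfarin". The data analysis plan (g.ii) adds that the sample is at higher risk, "hence a negative result will suggest very low risk in the general population".

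**The concern.** Censoring normally keeps a participant's follow-up and events up to the censoring date. Here the word triggers removal of the whole record. A participant with documented ARN whose anticoagulant is later withdrawn is then no longer a case, and no longer a participant either.

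This matters because the reason for removal may be linked to the outcome. The protocol does not describe withdrawal after AKI. It does make sure that the treating physician learns of every AKI and carries out a work-up, so more frequent withdrawal in cases than in non-cases is plausible. The reported incidence would then be biased downward, towards the hypothesis of a lower incidence than with warfarin and towards the reading of a negative result as very low risk. Because the records are removed, the study database could not show afterwards whether this had happened.

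**Working it through.** **Inputs.** Planned sample 40 (section 5.b). The protocol's own scenarios are 0, 2 and 10 cases in 40 (g.ii). Withdrawal rates are not given. Let f be the rate in cases and w the rate in non-cases; every value of f and w below is an assumption.

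**Step 1: the plan's own figures.** Exact (Clopper–Pearson) 95% intervals:

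| Cases/N | Protocol | Recomputed |
|---|---|---|
| 0/40 | 0–9% | 0–8.8% |
| 2/40 | 5% (0.6–17%) | 5.0% (0.6–16.9%) |
| 10/40 | 25% (13–41%) | 25.0% (12.7–41.2%) |

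The stated intervals are right. They describe 40 retained participants.

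**Step 2: effect of deletion.** With C cases and N non-cases, and deleted participants leaving both numerator and denominator:

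reported incidence = C(1−f) / [C(1−f) + N(1−w)]

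This equals C/(C+N) when f = w, is lower when f > w, and is higher when f < w.

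**Step 3: the 10/40 scenario (C = 10, N = 30).**

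| f | w | Retained | Reported | Exact 95% CI |
|---|---|---|---|---|
| 50% | 10% | 5/(5+27) = 5/32 | 15.6% | 5.3–32.8% |
| 20% | 10% | 8/(8+27) = 8/35 | 22.9% | 10.4–40.1% |
| 20% | 20% | 8/(8+24) = 8/32 | 25.0% | 11.5–43.4% |
| 0% | 20% | 10/(10+24) = 10/34 | 29.4% | 15.1–47.5% |

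The first two rows are biased downward, the third loses precision only, and the fourth is biased upward.

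**Step 4: the 2/40 scenario.** If anticoagulation is withdrawn in both cases and in no non-case, 0/38 remains. The upper limit is 1 − 0.025^(1/38) = 9.3%, against 16.9% for 2/40. This is close to the protocol's zero-case scenario: "If the incidence is zero, Stata calculates the 95% confidence interval based on our sample size as 0-9" per cent. If withdrawals in the two cases are independent, the chance that both are deleted is f²: 6% for f = 25%, 25% for f = 50%, and 56% for f = 75%.

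**Step 5: the denominator.** The planned Stata command is written with 40. If 40 is kept after deletions, every deleted case lowers the estimate whatever w is. With f = w = 20% the result is 8/40 = 20.0% (9.1–35.6%) instead of 25%. With f = 0 it stays at 10/40 = 25%, so the upward bias of the last row above disappears.

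**The case against.** The best counter-reading is that only someone still at risk can be censored. A participant with documented ARN has already reached the endpoint, so the deletion would touch only event-free participants. The text does not support this. The trigger covers any clinical reason, and the consequence clause already departs from the usual meaning of censoring by removing all data.

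Other points have more force, and limit the claim without removing it.

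- **Size.** It is entirely assumed. Notification of the physician shows that outcome-related withdrawal is possible, not how often it occurs. The reduced intervals still cover the full-data values: 5/32 gives 5.3–32.8%, which includes 25%, and 0/38 gives 0–9.3%, which includes 5%.
- **Warfarin comparison.** In the 10/40 example the intervals before and after deletion both include 17%, the lower warfarin figure in g.ii, so that comparison is unresolved either way.
- **Direction.** That equal rates cost only precision holds when the denominator shrinks with the deletions; with a fixed 40 the estimate falls.
- **Source records.** The hospital record system and the laboratory keep their own data, so the evidence is not destroyed everywhere. Removal from the participant list does, however, take away the link to those records.
- **Estimator.** The choice of incidence estimator can be left to an analysis plan. The deletion rule cannot, because an analysis plan cannot use records that the protocol has removed.

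**Conclusion.** The concern holds. As written, the protocol removes recorded primary-endpoint events whenever anticoagulation is later withdrawn for a clinical reason. This is a stated rule, not an omitted detail, and it conflicts with the aim of finding what proportion develop ARN.

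The direction of bias depends on withdrawal rates that the protocol does not give. With the denominator reduced by the deletions, it is downward if cases are withdrawn more often, absent if the rates are equal, and upward if non-cases are withdrawn more often. On the assumed rates, a 25% incidence could be reported as anything from 15.6% to 29.4%. The consequence is greatest when events are few: losing two cases turns 5% into zero and brings the upper limit down from 16.9% to 9.3%. The point must be fixed before any participant's data are removed.

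**What to change.** 1. Rewrite Withdrawal of Subjects (i.ii) so that all data and events up to the date of anticoagulant withdrawal are kept, and data are deleted only at the participant's own request.
2. Count as an event any AKI recorded on or before withdrawal that the work-up confirms as ARN, even if the work-up finishes later.
3. Compute the estimate and its interval on the participants actually analysed, not on a fixed 40.
4. Report the number, timing and reasons of withdrawals, separately for participants with and without AKI.
5. Name in advance one method for incomplete follow-up in the 6-month cumulative incidence. The protocol's word censored points to a Kaplan–Meier estimate, with censoring at withdrawal when there is no prior AKI. That estimate assumes withdrawal is unrelated to risk; a competing-event estimate, which answers a different question, can be the sensitivity analysis.
6. State whether a change to another anticoagulant counts as withdrawal for this data rule.

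Items 1 to 4 are essential; 5 and 6 are secondary. The cost is protocol wording, a check that the consent text agrees, and slightly more analysis. No visits, tests or payments are added; the only later information needed is the result of a work-up already under way, which the protocol already sends to the research team. Clinical decisions about anticoagulation are unaffected.
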